4.6. Randomization and Stratification: Personnel in the Department of Biostatistics and Bioinformatics at Emory University have developed a centralized electronic randomization system that has been successfully used in several clinical studies¹⁶⁻¹⁹. Subjects will be blindly assigned in equal proportions, stratified by age (above and below 58 years) using a pseudo-random-number generator with randomly permuted blocks. These assignments will be stored in a backend database table within the iDataFAX database management system. This method serves to balance the treatment group assignments over the course of the study to ensure that the desired number of subjects will be allocated to each of the treatment groups at any time point during the randomization period. Permuted block sizes will not be disclosed to the blinded study personnel to minimize the likelihood of their being able to predict the next randomization assignment in the series. Briefly, after obtaining informed consent, all eligibility confirmation data will be entered into the web-based data management system by a research coordinator. If the patient meets all eligibility criteria, computer randomization will be performed and the coordinator will be provided with an audit trail of the process including a verifiable link between the unique study ID and treatment assignment. The application will be password protected with access restricted to designated personnel, including the EUH Investigational Drug Pharmacy staff pharmacist who **will dispense blinded study drug for subjects randomized to Arms A or B.**

4.7. Screening, Entry and Follow-up Evaluations: These will occur as outlined in Table 1. Adverse effects and safety data will be reviewed at least every 6 months by a Data Safety Officer, a gastroenterologist senior Emory faculty member with expertise in clinical trials who is unaffiliated with the study, as described below (Section 7.5).

4.8. Procedures to be performed (all for research purposes only):

- **Medical examination:** Medical history and medications will be reviewed by a member of the research team, and a physical exam will be completed by a licensed physician, as required by the clinical research unit. Habitual alcohol intake and dietary calcium intake (based on reported supplements, dairy, and other high-calcium foods) will be assessed.
- **Urine collection:** Urine will be collected for standard urinalysis indexes.

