Study drug tolerance will be assessed by obtaining serial measures of the Gastrointestinal Symptom Rating Scale (GSRS) every two weeks during the 12-month placebo or probiotic regimen²¹. These will be obtained with in-person interviews at the baseline and month 6 and 12 visits and by telephone contact with all subjects by the study coordinator every 2 weeks. Data will be analyzed within the 5 symptom domains depicting symptoms related to gastric reflux, abdominal pain, indigestion, diarrhea, and constipation. A GSRS total score, the sum of all 5 domains, will also be assessed. To our knowledge there is no published absolute or change in the GSRS score that is demonstrative of intolerance to a study drug or other treatment²¹⁻²³. Therefore we will *a priori* define intolerance to the study drug as a 50% increase in the total GSRS score from baseline at any two consecutive time points, or the new onset of a GSRS classifier score of 2 or 3 in at least three of the 15 gastrointestinal symptoms queried. If either of these signs of intolerance occurs, we will offer the subject the options of: 1) discontinuing from the study; 2) discontinuing the study drug but participating in the serial assessments (e.g. blood draws, DXA) in the research center, or 3) decreasing the dose of blinded study drug to one sachet/daily, with the option of resuming the two sachet/day study regimen upon resolution of symptoms. If intolerance symptoms recur, the same strategy will be followed. All episodes of intolerance to study drug and the twice-monthly GSRS data will be recorded by the study coordinator in the individual subject case report forms (CRFs) (see below).

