Compliance with the study placebo or VSL#3 doses will be assessed serially. This will be determined by contacts (twice monthly telephone or at research center visits) of the study coordinator with each subject and responses to three standardized question areas: 1) "Are you having any difficulty, problems or new symptoms with the study medication?" 2) If yes, "What has the problem been?" and 3) "Have you missed any of your study drug doses, and if so how many in the previous 2 week period?" Appropriate notations based on subject responses will be documented in the CRF. Subjects will be instructed at study entry and reminded via serial contacts to return all of their used and unused drug sachets at each CRN visit (6 months +/- 2 weeks and 12 months +/- 2 weeks after entry). Unused and used study drug sachets will be tallied and recorded in the CRF by the study coordinator serially for the entire study. All sachets (used and unused) will be given to the Emory University Investigational Drug Service (IDS) for disposal.

Recruitment and retention will be documented via conventional CONSORT criteria and documentation of missed study visits, missed telephone communications and compliance with study drug administration. All data will be maintained in the CRFs.

4.13. Sample size and power considerations: Longitudinal data from 380 postmenopausal women form the basis for estimating the sample size and power for lumbar spine BMD as the primary outcome endpoint. BMD at the lumbar spine was available at baseline and 6 and 12 months after baseline (883 measurements across the 3 time points). Mean baseline BMD was 1.108 g/cm² (within-subject standard deviation = 0.03 g/cm² and the standard deviation on change = 0.02 g/cm²). Assuming no decline on average in BMD in the VSL#3 treated group and a decline on average of 0.03 g/cm² in the control group and an estimated within-subject standard deviation in each group of 0.03 g/cm², the proposed sample sizes (n=20 postmenopausal women per group) will provide more than 85% power to detect a difference on change of 0.03 g/cm² at the two-sided 5% significance level if the true difference between treatment groups is 0.03 g/cm² (two-sided two-sample equal variance t-test).

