4.14. Statistical analyses: Demographic data will be summarized with standard descriptive statistics. Repeated-measures analyses for each outcome (i.e., GSRS scale scores, BMD) will be performed with a means model via the SAS MIXED Procedure (version 9.4; SAS Institute, Cary, NC), providing separate estimates of the means by time on study (baseline, 1-year and 2-years) and treatment group. The model will include three predictors (treatment arm, time on study and the statistical interaction between treatment arm and time on study). A compound-symmetric variance-covariance form in repeated measurements will be assumed for each outcome and robust estimates of the standard errors of parameters will be used to perform statistical tests and construct 95% confidence intervals²⁴. The model-based means are unbiased with unbalanced and missing data, so long as the missing data are non-informative (missing at random, MAR). A P-value ≤0.05 will be considered statistically significant for the main effects (treatment and time on study) and for the treatment by time on study interaction effect from the repeated measures analysis. The statistical test for interaction between time on study and treatment will be the primary overall hypothesis test to determine whether an outcome in the two study groups changed in significantly different ways during follow-up (i.e., different temporal patterns over time). If a mean outcome in the two groups is consistently different or similar over time (i.e., no statistical interaction) then the main effect test for treatment will be used as the primary test of VSL#3 efficacy. If a significant interaction is detected, then t-tests will be used to compare the differences between the model-based intervention means at each time point and to compare differences over time within each treatment arm. Specific statistical tests will be done within the framework of the mixed effects linear model. Analyses will control for risk factors for osteoporosis, such as age, gender, race, BMI, habitual alcohol consumption, smoking, physical activity, and fracture history, as necessary. All tests will be 2-sided and a P value ≤ 0.05 will be considered significant.

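### Section 4.14 uses robust standard errors with 20 women per arm and names no small-sample correction: the excess false-positive rate is slight for BMD and, for GSRS, depends on a time factor the plan leaves unclear

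*Combined protocol and SAP*

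**What the plan says.** Section 4.14 sets one approach for all outcomes: "Repeated-measures analyses for each outcome (i.e., GSRS scale scores, BMD) will be performed with a means model" in SAS MIXED, with arm, time and their interaction as predictors and a compound-symmetric working covariance. On inference it says that "robust estimates of the standard errors of parameters will be used to perform statistical tests" and to form 95% intervals. It does not say which robust estimator, which small-sample correction or which denominator degrees of freedom.

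The arm-by-time interaction is the primary test for each outcome. If there is no interaction, the treatment main effect becomes the efficacy test. Risk factors are to be adjusted for as needed. The significance rule is: "All tests will be 2-sided and a P value ≤ 0.05 will be considered significant".

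The time levels written in 4.14 are baseline, one year and two years. Treatment lasts one year (section 5.3) and the last visit is at 12 months (Table 1). DXA is done twice, at screening or entry and at 12 months (Table 1, section 8). CTX, PINP and the cytokines are measured at entry, 6 and 12 months (Table 1). Tolerance is assessed by "obtaining serial measures of the Gastrointestinal Symptom Rating Scale (GSRS) every two weeks" (section 4.10).

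**The concern.** The classical sandwich variance is biased downward when there are few independent subjects. The effect of this grows with the number of parameters tested jointly and with the number of between-subject covariates. With 40 women and no stated correction, P values would be too small and intervals too narrow. How much this matters depends on the test: a one-parameter BMD contrast is hardly touched, whereas a joint test of many GSRS time points could be badly affected. The sample-size calculation in section 4.13 assumes an equal-variance t-test, which has exact size under normality. The planned robust test does not share that property.

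**Working it through.** **Inputs.** n = 20 per arm and two-sided 5% (sections 4.13, 4.14). BMD has 2 occasions and the turnover markers and cytokines have 3 (Table 1). GSRS every two weeks for 12 months gives 24 to 26 contacts plus baseline, so 25 to 27 occasions (section 4.10).

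**The plan's own figure.** Section 4.13 says that "the proposed sample sizes (n=20 postmenopausal women per group) will provide more than 85% power". The target is a between-arm difference in BMD change of 0.03 g/cm², and the SD entered for each arm is also 0.03 g/cm². The noncentrality is 0.03 / (0.03 × √(2/20)) = 3.162. With 38 df and critical value 2.024, the power is 86.9%. The stated figure reproduces, but for a t-test and not for the robust test of 4.14.

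**Two-visit BMD interaction.** With complete balanced data the classical sandwich variance is (n−1)/n = 19/20 of the unbiased one. The robust t is therefore the ordinary t times √(20/19) = 1.026.
- t cutoff, 38 df: P(|t38| > 2.024/1.026 = 1.973) = 5.6%.
- Normal cutoff: P(|t38| > 1.960/1.026 = 1.910) = 6.4%.
- Interval width with the t cutoff: √(19/20) = 0.975 of the correct width, so about 3% too narrow.

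**Joint interaction with T time levels.** Let q = T − 1. The Wald statistic is 20/19 times Hotelling's T² with 38 df. The null rejection rate at cutoff c for W/q is

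P{ F(q, 39−q) > c × (19/20) × (39−q)/38 }.

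The cutoff c comes from F with between-within df, 38 × (T−1), from F with 38 df, or from chi-square. Two examples with between-within df:
- T = 3: c = 3.117; threshold 3.117 × 0.95 × 37/38 = 2.883; P(F(2,37) > 2.883) = 6.9%.
- T = 27: c = 1.507; threshold 1.507 × 0.95 × 13/38 = 0.490; P(F(26,13) > 0.490) = 94%.

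| Time levels | Between-within df | 38 df | Chi-square |
|---|---|---|---|
| 2 (BMD) | 5.6% | 5.6% | 6.4% |
| 3 | 6.9% | 6.2% | 7.6% |
| 7 | 13.7% | 10.4% | 14.5% |
| 13 | 33.4% | 24.3% | 34.3% |
| 25 | 89% | 81% | 89% |
| 27 | 94% | 88% | 94% |

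Simulation agreed at 27 levels under compound-symmetric, autoregressive and skewed data: 94-95% with between-within df, 88-90% with 38 df. With 10% of visits missing it gave 6.8% at three levels and 94.5% at 27 (between-within df). Skewed data gave somewhat lower rates at three levels (5.3-6.6%).

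**Covariates.** Section 4.14 lists eight risk factors. Gender is constant here, which leaves 7. Section 4.1 adds baseline BMD at three sites and co-morbidities, so 7 + 3 + 1 = 11. Null simulations with n = 40 and an uncorrected sandwich gave:
- Two-visit interaction: 5.2% with 7 covariates and 5.4% with 11, against 5.9% with none in the same runs (exact 5.6%). Person-level main effects drop out of the within-woman change when data are complete.
- Treatment main effect: 8.9-9.7% with 7 covariates and 11.0-11.5% with 11. The model-based test gave 5.0% and 4.9%.

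**The case against.** The strongest reply is that the primary endpoint is barely affected: 0.6 of a percentage point on the BMD interaction. That stands, and it is why this is not a must-fix.

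A reader might infer that the GSRS interaction will be falsely positive in about 90% of null trials. The documents do not support that. Section 4.14 writes three time levels for each outcome, and nothing says that each two-weekly score becomes its own level. At three levels the rate is 6-8%. Still, the written levels cannot be followed in a 12-month trial, so they do not restrict the GSRS times either. The high figure remains a possibility that the plan leaves open.

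A reader might also infer that the tolerance conclusion would be wrong in nearly every null trial. Section 4.10 defines intolerance for each woman by her own score changes, without using the interaction test.

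Nor does covariate adjustment inflate the primary BMD interaction to 9% or more. That inflation belongs to the fallback main-effect test, and because 4.14 adjusts only as needed, entering all 11 covariates together is an upper case.

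Finally, the absence of a correction is inferred from silence. A corrected sandwich may be intended, but the plan should then say so.

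**Conclusion.** The point holds at moderate severity. If the classical sandwich is used, every affected test runs above 5%: trivially for the primary BMD interaction, modestly for three-visit outcomes, and to about twice nominal for the BMD fallback test with many covariates. For GSRS the plan permits anything from about 6% to 94%, depending on an undefined time factor. The GSRS extreme applies only to the many-parameter joint test; single GSRS contrasts are off by about one point, as for BMD.

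The exact figures assume normal complete data, equal covariance in the arms and 20 women per arm. No dropout rate is given; with an assumed 16 per arm the BMD figure is 5.7% (t cutoff).

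**What to change.** In section 4.14:
1. For BMD and three-visit outcomes, replace the robust standard errors with REML, an unstructured covariance and Kenward-Roger degrees of freedom. A named small-sample-corrected sandwich is an acceptable alternative for these outcomes.
2. For GSRS, replace the many-parameter interaction with one prespecified between-arm contrast: mean on-treatment score minus baseline. In simulation this held 5.2-5.4% under both compound-symmetric and decaying correlation. Rescaling the sandwich by n/(n−1) would not do here, since it leaves about 93% at 27 levels (between-within df). Nor would model-based compound-symmetric tests, which gave 16% at 27 levels under autoregressive correlation of 0.8.
3. Correct the time levels to match the visit schedule, outcome by outcome.

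The cost is plan wording and a few lines of code before unblinding. No new data are needed. BMD intervals become about 3% wider (√(20/19) = 1.026).

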The study will be conducted in a population of ambulatory, postmenopausal women aged 50-65 (BMI >18.5 and $\leq 30 \text{ kg/m}^2$), with a lumbar spine (L1-L4), femoral neck, and total hip BMD T-score > -2.5, as measured by DXA (see section 3 above). Women with osteoporosis (T score ≤ -2.5) will not be included in the study because at this stage of knowledge we find it unethical not to offer effective treatment to these individuals. We will recruit subjects of all ethnic groups. Covariates known to influence bone mass, including body mass index (BMI), history of smoking > 6 months prior to entry, alcohol use, baseline BMD of the lumbar spine, femoral neck and total hip area, bone fracture history and co-morbidities will be collected and controlled for in the final analysis. The primary endpoint is the change in bone mineral density (BMD) at the L1-4 lumbar spine over one year of study. Changes in BMD at the femoral neck and total hip area will be secondary endpoints. All BMD data will also be used as a tool for future studies power calculation and design. Additional endpoints will include changes in bone turnover markers and inflammatory/osteoclastogenic cytokines. These indices will provide much needed mechanistic information. To determine additional potential mechanisms of action of probiotics on health, we will conduct serial metabolomics analyses in the plasma, as well as serial assessment of plasma thiol/disulfide redox balance. The data will allow us to establish whether VSL#3 prevents bone loss and/or increases bone mass by regulating bone resorption, formation, or both. Based on our own data in mice following ovx, we hypothesize that treatment with VSL#3 will quickly decrease bone resorption and then stimulate bone formation, resulting in improved net BMD at least one site over the 12-month period of study.

4.2. Screening for eligibility: For study subjects identified among patients seen at the Emory-affiliated Endocrinology, Ob/Gyn, Rheumatology and General Medicine clinics, patients will be pre-screened for eligibility using the Emory Healthcare electronic medical record, and potentially eligible subjects will be approached during their clinic visit by a study coordinator or they will be contacted by phone or letter (as described above) to conduct a full screen. For potential study subjects identified outside of Emory-affiliated Clinics, potential subjects will contact the study team by phone and undergo a pre-screening discussion.

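### Section 4.14 lets the primary BMD claim be won on either of two tests, each at two-sided 5%: under its three-predictor model the overall error is about 9.75%, and the second test is not a test of change

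*Combined protocol and SAP*

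**What the plan says.** Sections 4.1 and 4.9 declare the primary endpoint as change in L1-L4 spine BMD. Table 1 and section 8 schedule one DXA at screening or entry and one at 12 months. Section 4.13 sizes the trial for a single two-sided 5% t-test on that change.

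Section 4.14 sets out the analysis:

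- "The model will include three predictors (treatment arm, time on study and the statistical interaction between treatment arm and time on study"), with compound symmetry and robust standard errors.
- Baseline is one of the modelled times: "providing separate estimates of the means by time on study (baseline, 1-year and 2-years) and treatment group".
- "The statistical test for interaction between time on study and treatment will be the primary overall hypothesis test".
- If there is no interaction, "then the main effect test for treatment will be used as the primary test of VSL#3 efficacy".
- A P-value of 0.05 or less "will be considered statistically significant for the main effects (treatment and time on study) and for the treatment by time on study interaction effect". The section ends: "All tests will be 2-sided and a P value ≤ 0.05 will be considered significant".

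On baseline BMD the sections differ. Section 4.1 says that "baseline BMD of the lumbar spine, femoral neck and total hip area, bone fracture history and co-morbidities will be collected and controlled for". Section 4.14 has three predictors and then adds: "Analyses will control for risk factors for osteoporosis, such as age, gender, race, BMI, habitual alcohol consumption, smoking, physical activity, and fracture history, as necessary". Baseline BMD is not on that illustrative list.

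**The concern.** Two tests are called primary, and the second is reached because the first failed. That is the reverse of a gatekeeping order, in which a failed first test closes the door. No alpha split, closed test or other multiplicity rule appears anywhere in the document.

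Two things are at stake. The stated 5% level may not hold for the primary claim. And a non-significant result on the declared endpoint would not count as a negative trial, because another test could still be reported as the primary evidence of efficacy. Under the three-predictor model that other test includes baseline BMD, which treatment cannot affect, so a chance imbalance at entry among 40 women could become the efficacy result.

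**Working it through.** **Inputs.** 20 women per arm, effect 0.03 g/cm², two-sided 5% (section 4.13); two DXA times (Table 1, section 8); compound symmetry and robust standard errors (section 4.14). The between-subject SD is not in the documents; I assume 0.05–0.16 g/cm². For the SD of change I use 0.02–0.042. Section 4.13 gives 0.02, its t-test figure reproduces with 0.03, and its within-subject SD of 0.03 implies 0.03 × √2 = 0.042 under compound symmetry.

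**1. The plan's own figure.** Noncentrality = 0.03 / (0.03 × √(2/20)) = 3.16. On 38 df the power is 86.9% (normal approximation 88.5%), which agrees with the stated figure of more than 85%. It is the power of one test.

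**2. Three-predictor model.** Let Y0 and Y12 be the two BMD values. The interaction tests the arm difference in D = Y12 − Y0. The main effect tests the arm difference in M = (Y0 + Y12)/2.

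- Cov(D, M) = ½[Var(Y12) − Var(Y0)] = 0 under compound symmetry.
- Overall error = 0.05 + 0.95 × 0.05 = 9.75%, whatever the SDs.
- Simulation with ordinary t-tests gives 9.5–9.9%. False claims of benefit are about half of that, 4.8–4.9% against the intended 2.5%.
- With uncorrected robust standard errors and a t reference, the two-step rate is about 11% (10.7–11.0%).

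**3. What the fallback can detect.** A 12-month effect of 0.03 is halved to 0.015 in M. With SD of change 0.03, SD(M) = √(between-subject SD² + 0.03²/4).

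- Between-subject SD 0.05: SD(M) = 0.0522, noncentrality 0.015 / (0.0522 × 0.316) = 0.91, power 14%.
- Between-subject SD 0.16: SD(M) = 0.1607, noncentrality 0.30, power 6%.

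So the fallback alone has 6–14% power, against a 5% false-positive rate. Under the null, about half of the results that are significant only through the fallback point opposite to the observed difference in change.

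**4. Baseline BMD as a plain covariate, with baseline still a response level.** The main effect becomes half of the baseline-adjusted 12-month difference. Its correlation with the test on D is √((1 + ρ)/2), where ρ is the within-woman correlation. Example: between-subject SD 0.10 and within-subject SD 0.03 give ρ = 0.0100/0.0109 = 0.917 and a correlation of 0.979. The chance of at least one false positive is 5.95% in large samples and 6.0% simulated at 20 per arm. Over the assumed range the rate is about 5.6–6.9% with model-based standard errors and about 6.5–8% with uncorrected robust ones.

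**5. Baseline BMD crossed with time, or 12-month BMD as the only response.** In the first case the interaction and the main effect become the same baseline-adjusted test; in the second only one test exists. The simulated rate for the crossed version is 4.9–5.1%.

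**6. One test alone.** With ordinary t-tests, a single test on change, plain or adjusted for baseline BMD and age stratum, rejects 4.9–5.1% under the null. With uncorrected robust standard errors at n = 40, the plain test rejects about 5.5% and the baseline-adjusted test about 6%.

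**The case against.** The strongest reply is that section 4.1 already commits to controlling for baseline BMD, and that done in one natural way this leaves no inflation. That stands. A reader might infer that the 5% level is broken however baseline BMD is handled; step 5 shows that it is not, and section 4.1 does not exclude that version. But the plan does not specify it either: section 4.14 keeps baseline as a response level, fixes three predictors and adjusts only where judged necessary.

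A reader might also infer that the second test is the only source of excess error, so that deleting it restores 5%. The document does not support that, because section 4.14 plans robust standard errors and states no small-sample correction. Step 6 shows a smaller excess for one test alone.

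It may be said that the fallback applies only when the arms are consistently different or similar over time. Section 4.14 equates that with the absence of a statistical interaction, and its only criterion is the 0.05 threshold.

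Finally, section 4.14 names three time levels. The DXA schedule supports two. With three levels the three-predictor rate would still be about 9.8–9.9%; the plain-covariate rate would be about 7.7–7.9%.

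**Conclusion.** The point holds for the analysis as section 4.14 writes it. Two primary tests at 5% each give an overall two-sided error of about 9.75% with model-based standard errors, or about 11% with uncorrected robust ones, and the second test does not address the declared endpoint. The 9.75% needs only compound symmetry and two DXA times. If age is assumed to shift baseline by −0.03 and change by 0.01 g/cm² and the stratum is left out, it falls to 8.8–9.6%.

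The size depends on what section 4.1 means. With baseline BMD as a plain covariate the excess is modest (about 5.6–6.9% model-based, about 6.5–8% uncorrected robust) and rests on an assumed between-subject SD. With baseline BMD crossed with time, or only 12-month BMD as the response, the second test adds nothing. The plan does not say which applies, and that also needs settling.

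**What to change.** - Delete the main-effect fallback for BMD.
- Name one primary test at two-sided 5%: the between-arm difference in L1-L4 BMD change from baseline to 12 months. State that a non-significant result on it is a negative primary result.
- Reconcile sections 4.1 and 4.14 on baseline BMD, preferably by adjusting this contrast for baseline BMD and the age stratum used in randomisation. The adjustment is a preference, but it settles the ambiguity.
- Specify model-based or small-sample-corrected standard errors for this test. With uncorrected robust ones, even the single test rejects about 5.5–6.2% under the null.
- Correct the time levels in section 4.14 to match the DXA schedule.

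The cost is wording and a little power. With effect 0.03 and SD of change 0.03 g/cm², the adjusted test has about 86–88% power, still above the stated 85%. The two-step rule has 87.8–88.7% under the three-predictor model and 88.1–90.2% with baseline as a plain covariate, so the loss is at most about 2 points. At an SD of change of 0.02 the loss is 0.2 point or less; at 0.042 it is 0.9–3.0 and 3.1–3.9 points respectively. Section 7.5.6 keeps the arms blinded until the endpoints have been analysed, so the change can be made before unblinding.

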- **Handgrip strength:** A small, handheld dynamometer will be used to measure grip strength. Participants will be asked to squeeze the instrument as hard as they can for 3 seconds, which will measure the pounds of force applied.
- **Questionnaires:** Participants will be asked to answer a standardized, validated questionnaire (15 questions) about GI symptoms segregated into 5 symptom domains (see below). They will also complete a questionnaire assessing their habitual physical activity (Modified Baecke Questionnaire)²⁰.

4.9. Primary Endpoint: The **primary endpoint is** change in BMD of the lumbar spine (L1-L4 segment), as measured by DXA.

4.10 Secondary Endpoints (please see Table 1 above): Serial measures of: 1) bone density of the non-dominant hip (femoral neck and total hip area) as measured by DXA, 2) serum collagen type 1 cross-linked C-telopeptide (CTX) concentrations (a marker of bone resorption), 3) serum procollagen type I N propeptide (PINP) concentrations (a marker of bone formation), 4) serum free receptor activator of nuclear factor kappa-B ligand (RANKL) concentrations, 5) serum osteoprotegrin (OPG) concentrations, 6) serum tumor necrosis factor- α (TNF α), 7) serum interleukin-17 (IL-17) concentrations, 7) total and regional body fat (including visceral fat) and lean body mass as measured by DXA and BIA, 8) plasma thio/disulfide redox biomarkers, 9) compliance with study drug administration 10) overall study recruitment and retention, and 11)) **stool microbiota composition**. Measurements of indices of bone turnover and cytokine levels will provide much needed mechanistic information to establish whether VSL#3 may prevent bone loss and/or increases bone mass by regulating bone resorption, formation, or both. Based on animal data, we hypothesize that treatment with VSL#3 will quickly decrease bone resorption and then stimulate bone formation.

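### After a significant interaction, section 4.14 tests the arms' mean levels at each time point and does not name the between-arm difference in change as the reported effect

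*Combined protocol and SAP*

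**What the plan says.** - **Endpoint.** Section 4.9 defines the primary endpoint as "change in BMD of the lumbar spine (L1-L4 segment), as measured by DXA". Section 4.1 says the same and sets the period at one year.
- **Power.** Section 4.13 states "power to detect a difference on change of 0.03 g/cm²" with 20 women per arm, from a two-sample t-test.
- **Primary test.** Section 4.14 fits a repeated-measures means model with arm, time and their interaction. The interaction is the primary test.
- **Follow-up.** If the interaction is significant, "t-tests will be used to compare the differences between the model-based intervention means at each time point". The same sentence adds comparisons over time within each arm. Baseline is one of the time points that section 4.14 lists.
- **Covariates.** Section 4.1 lists baseline BMD among the factors to be controlled for in the final analysis. The list in section 4.14 omits it. That list is offered as examples, to be used where needed.
- **Visits.** Table 1 and section 8 schedule DXA at screening or entry and again at 12 months. Bone turnover markers and cytokines are measured at entry, 6 and 12 months.

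**The concern.** Two kinds of follow-up comparison are named, and neither is the between-arm difference in change. The visit-by-visit tests compare levels, so without baseline adjustment they carry the full spread of BMD across women, which the change removes. They also test baseline, where any difference between randomised arms is due to chance. The within-arm tests do not compare the arms: a significant change in one arm and a non-significant change in the other is not evidence of a treatment difference.

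What is at stake is how a positive result is read. A significant interaction could be followed by a table showing no significant difference between arms at 12 months, and sometimes a lower VSL#3 mean, although the trial has found the effect it was designed to find.

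**Working it through.** **Inputs from section 4.13.** 20 women per arm; test "at the two-sided 5% significance level"; "a decline on average of 0.03 g/cm² in the control group" and none on VSL#3, so the planned difference is 0.03 g/cm². The power calculation uses "an estimated within-subject standard deviation in each group of 0.03 g/cm²". The source data also give "the standard deviation on change = 0.02 g/cm²".

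**Assumed input.** The SD of lumbar BMD across women at a single visit is not given. I take 0.12 g/cm², with a range of 0.08 to 0.16.

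**Formula.** SE = SD × √(2/20); noncentrality = 0.03/SE; power from the noncentral t with 38 df (critical value 2.024).

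**Step 1: the plan's own figure.** With SD 0.03, SE = 0.00949, noncentrality = 3.16 and power = 86.9%. This agrees with the stated figure of more than 85%. With the SD of change of 0.02, SE = 0.00632, noncentrality = 4.74 and power = 99.6%. If 0.03 is instead a per-measurement SD, the SD of change is √2 × 0.03 = 0.042 and power is 58.7%.

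**Step 2: level test at 12 months, no baseline adjustment.**

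| SD across women | SE | Noncentrality | Power |
|---|---|---|---|
| 0.08 | 0.0253 | 1.19 | 21.2% |
| 0.12 | 0.0379 | 0.79 | 12.0% |
| 0.16 | 0.0506 | 0.59 | 8.9% |

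The choice of 0.12 is not critical. The level test reaches 80% power only if the SD is about 0.033 (3% of the stated mean of 1.108), and drops below 50% once the SD exceeds about 0.047.

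**Step 3: what a reader would see after a positive primary test.** I simulated 40,000 trials per setting, with SD of change 0.02 or 0.03, and kept those with a significant interaction favouring VSL#3. The 12-month level test was also significant in about 22%, 12% and 9% of them at SD 0.08, 0.12 and 0.16. The VSL#3 mean lay below placebo in about 11%, 21% and 27%. It was significantly below in under 1%.

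**Step 4: level test with baseline adjustment.** The correlation between visits is ρ = 1 − c²/(2s²), where c is the SD of change and s the SD across women. The residual SD is s√(1 − ρ²). With s = 0.12 and c = 0.03, ρ = 0.969, the residual SD is 0.0298, and power with 37 df is 87.4%. With c = 0.02 it is 99.6%.

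**Step 5: degrees of freedom of the interaction.** For BMD, two arms and two visits give (2 − 1)(2 − 1) = 1 df, which is the difference in 12-month change. For the markers, three visits give (2 − 1)(3 − 1) = 2 df. A significant result there does not say at which visit the changes differ, and no planned between-arm contrast isolates the change to 6 or to 12 months.

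**The case against.** The strongest reply is that change is already tested. With two DXA visits, the interaction is the between-arm comparison of 12-month change, so endpoint, power calculation and primary test agree. A reader might infer from the follow-up sentence that the plan tests levels in place of change; for BMD it does not. The level tests come after the primary test, and no efficacy decision depends on them.

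A reader might also infer that the follow-up can contradict the primary result. A non-significant difference in levels beside a significant difference in change is not a contradiction, and a significant reversal occurs in under 1% of the simulated trials.

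Section 4.14 does provide for 95% confidence intervals on model parameters, and the interaction is one of these. The interval will therefore be available for BMD. What is missing is its designation as the reported effect.

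The reply from section 4.1 also has force: adjusting for baseline BMD brings the 12-month comparison back to about 87% power or more. But section 4.14 names three predictors, leaves baseline BMD off its covariate list and treats baseline as an outcome visit. The adjusted comparison is promised in one section and not specified in the other.

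Finally, comparing arms visit by visit after a significant interaction is conventional. That does not help here, because the outcome varies far more between women than within them.

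**Conclusion.** The primary test for BMD is sound on this point. The planned interpretation of a positive result is not well matched to it: the between-arm follow-up is on levels, includes baseline, and leaves the difference in change unnamed as the reported effect. Without baseline adjustment, the 12-month level test has roughly 9% to 21% power for the planned effect, against 86.9% for the change contrast at SD 0.03. It would usually be non-significant after a positive primary test, and could look inconsistent with it without overturning it.

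The 9% to 21% is not a figure from the plan. It rests on an assumed SD of 0.16 to 0.08 g/cm², on 20 women per arm with complete data, and on no baseline adjustment. For the markers, the gap does not depend on any SD: the 2 df interaction leaves the change to each visit without a planned between-arm contrast.

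**What to change.** In section 4.14:

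1. Make the between-arm difference in change from baseline both the follow-up contrast and the reported effect, as an estimate with a 95% CI from the same model: at 12 months for BMD, and at 6 and 12 months for the markers. For BMD this is the interaction contrast itself.
2. Do not test the arms against each other at baseline.
3. Show arm means by visit as description only.
4. Reconcile the covariates with section 4.1 on baseline BMD. Either keep baseline as an outcome visit and report the difference in change, or take it out of the outcome and use it as a covariate. At SD of change 0.03 and SD across women 0.12, the two routes have similar power (86.9% and 87.4%), so the need is to state one.

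The cost is SAP wording and one ESTIMATE statement per outcome. Visits, data collection and sample size are unchanged.
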